9.2. Other safety endpoints

No other safety endpoints are foreseen in this study.

10. Exploratory analysis

In the course of this study, exploratory analysis is not envisaged.

11. Interim analysis

One interim analysis is planned to assess the primary and secondary efficacy endpoints when a group of patients with available data on the primary endpoint will include at least 200 subjects [100 patients in each treatment group: in the main treatment group of patients taking Ferrum Lek[®] (iron (III) hydroxide polymaltosate complex) and in the control group of patients taking MALTOFER[®] (iron (III) hydroxide polymaltosate complex]. Safety and efficacy will be assessed in all patients who have received at least one dose of randomized therapy at the time of the interim analysis. Based on the results of the interim analysis of the primary and secondary statistical endpoints of efficacy and safety, the Sponsor may decide to discontinue the study if the endpoints of the study are achieved in accordance with the protocol based on the results of the interim analyses or the sample size can be recalculated using the results of the interim analysis.

STATISTICAL ANALYSIS PLAN

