#### 2.3.6.4 Contraindications/Precautions

Ferrum Lek chewable tablets or syrup are contraindicated to patients with hypersensitivity to any of the drug components.

The drug is contraindicated to patients with excessive iron content or with disorders of iron utilization processes (hemosiderosis, hemochromatosis, lead anemia, sideroachrestic anemia, thalassemia), as well as with anemia not associated with iron deficiency.

The drug should not be prescribed to patients receiving repeated blood transfusion.

IPC should not be prescribed simultaneously with parenteral iron.

Precautions should be taken in patients with phenylketonuria (Ferrum Lek tablets contain aspartame, a source of phenylalanine in an amount equivalent to 1.5 mg/tablet).

Caution should be exercised in patients with diabetes mellitus. Insignificant increase in iron store concentration is associated with a significant increase in glucose homeostasis parameters [95].

Iron preparations are not used in patients with anemia caused by chronic inflammation or malignant neoplastic diseases, as iron is pooled in reticuloendothelial cells. Use of such iron to synthesize hemoglobin starts only after the elimination of pathology [96].

Oral iron drugs can color feces dark, but this effect is clinically insignificant.

There is data indicating that additional iron received by children without iron deficiency causes growth impairment [97].

If oral use of iron drugs was not successful, a possible reason could include incorrect diagnosis, a lack of compliance, constant bleeding, underlying infection, malignant neoplasms, liver disorders, and iron malabsorption.

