## Secondary efficacy endpoints:

- Absolute values and changes of blood hemoglobin level (g/L) after 4, 8 and 12-weeks of treatment in the study groups.
- Changes in average values of iron metabolism parameters (ferritin, transferrin, percent transferrin saturation, serum iron) after 4, 8 and 12 weeks of iron-deficiency anaemia treatment, as compared with the baseline value in the study groups.
- The frequency of response to therapy, determined as an increase in haemoglobin level by 20 g/L and more after 12-weeks of iron-deficiency anemia treatment in the study groups.
- Frequency and severity of all adverse events observed during the study therapy in the study groups.

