#### 9.1.4 Safety parameteres analysis

Safety evaluation will include:

- 1) determination of the total number, incidence and severity of the folowing:
  - I. adverse events (AEs), regardless of their relationship to the treatment;
  - II. AEs associated or potentially associated with the drug;
  - III. AEs leading to discontinuation.

2) Gastrointestinal disorders (determined by means of a standardized MedDRA query for the corresponding symptoms), regarded by the Investigator as related to the study therapy, will be analyzed separately.

Methods of descriptive statistics will be used to represent the results. A comparison of the incidence of new AE cases in the study groups will be performed using the Fisher's exact test or

the chi-square test, depending on the number of proposed observations in one cell (<5 or  $\ge 5$ ), and a comparison of the severity (and the possible causality between the study drug and AE) will be conducted using the Cochran—Armitage test for linear trends for ordered categorical data.

3) Changes in the results of laboratory studies (conducted in the central laboratory) over time and the incidence of abnormal results of studies (based on the reference values of the central laboratory) will be summarized by group, and a comparison will be made between the groups using appropriate tests for quantitative and qualitative data (see below).

4) Changes in the vital signs over time and the incidence of pathological abnormalities revealed during physical examination will be summarized by group, and a comparison will be made between the groups using appropriate tests for quantitative and qualitative data (see below).

Comparison of quantitative data will be conducted using the t-test or the Mann—Whitney test, depending on the distribution normality (which will be estimated using the Shapiro—Wilk test).

Qualitative data will be compared using the exact Fisher's exact test or the chi-square test, depending on the number of proposed observations in one cell (<5 or  $\geq 5$ ).

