SOP-05-02_RF01 Statistical Analysis Plan_01APR2020_3.0 Confidential Page 54 of 68

STATISTICAL ANALYSIS PLAN

Visit	Group	Parameter	Weight	Age	BMI	Height
		Beyond the limit of detection				
		Mean				
		95% CI				
		SD				
		Median				
		Min				
		Max				
		Q1.25%				
		Q3.75%				
		IQR.75%				
		Ν				
		Missed				
		Beyond the limit of detection				
		Mean				
	Treatment group:	95% CI				
	T – Ferrum Lek [®]	SD				
		Median				
		Min				
		Max				
		Q1.25%				
		Q3.75%				

STATISTICAL ANALYSIS PLAN

Visit	Group	Parameter	Weight	Age	BMI	Height
		IQR.75%				

Table 13. Physiological data, statistical test

Vi	V1				
Vari	Weight	Age	BMI	Height	
Shapiro– Wilk test, p-value	Treatment group: R – Maltofer [®]				
	Treatment group: T – Ferrum Lek [®]				
Student's t-					
Wilcoxon–Mann–W					

Table 14. Physiological data, categorical data

Visit	Variable	Group	Distribution of responses	Chi-square test, p-value
7/1	Conton	Treatment group: $R - Maltofer^{$		
V1	Gender	Treatment group: T – Ferrum Lek®		

Table 15. Biochemistry 1

Visit	Group	Parameter	ALT	AST	Total protein	Total bilirubin	C-reactive protein
V1	Treatment group:	Ν					
	$R - Maltofer^{\mathbb{R}}$	Missed					

STATISTICAL ANALYSIS PLAN

Visit	Group	Parameter	ALT	AST	Total protein	Total bilirubin	C-reactive protein
		Beyond the limit of detection					
		Mean					
		95% CI					
		SD					
		Median					
		Min					
		Max					
		Q1.25%					
		Q3.75%					
		IQR.75%					
		Ν					
		Missed					
		Beyond the limit of detection					
		Mean					
	Treatment group:	95% CI					
	I – Ferrum Lek	SD					
		Median					
		Min					
		Max					
		Q1.25%					

SOP-05-02_RF01 Statistical Analysis Plan_01APR2020_3.0

STATISTICAL ANALYSIS PLAN

Visit	Group	Parameter	ALT	AST	Total protein	Total bilirubin	C-reactive protein
		Q3.75%					
		IQR.75%					
		Ν					
		Missed					
		Beyond the limit of detection					
		Mean					
		95% CI					
	Treatment group: R – Maltofer®	SD					
		Median					
		Min					
1/5		Max					
V 5		Q1.25%					
		Q3.75%					
		IQR.75%					
		Ν					
		Missed					
	Treatment group:	Beyond the limit of detection					
	I – Ferrum Lek®	Mean					
		95% CI					
	·	SD					

SOP-05-02_RF01 Statistical Analysis Plan_01APR2020_3.0

STATISTICAL ANALYSIS PLAN

Visit	Group	Parameter	ALT	AST	Total protein	Total bilirubin	C-reactive protein
		Median					
		Min					
		Max					
		Q1.25%					
		Q3.75%					
		IQR.75%					

Table 16. Biochemistry 2

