Shapiro–	Shapiro– Treatment group: R – Maltofer [®]						
Wilk test, p-value	Treatment group: T – Ferrum Lek [®]						
Student's t-test, p-value							
Wilcoxon-Mann-W	/hitney test, p-value						

STATISTICAL ANALYSIS PLAN

Table 20. Biochemistry, statistical test 3

Visit		V1					
Variable		T4	Vitamin B12	Creatinine index	TSH	Folic acid (B9)	
Shapiro– Wilk test, p-value	$\begin{array}{l} Treatment \ group: \\ R-Maltofer^{\circledast} \end{array}$						
	Treatment group: T – Ferrum Lek [®]						
Student's t-test, p-value							
Wilcoxon–Mann–Whitney test, p-value							

STATISTICAL ANALYSIS PLAN

Adverse events	Group	Amount	% of the total number of AEs	% of the number of AEs by the medicinal product	p-value, Fisher's test
All adverse events	Т				
	R				
	Т				
SUC	R				
DT	Т				
F1	R				
DT	Т				
P1	R				
	Т				
	R				
SOC	Т				
	R				
РТ	Т				
	R				
РТ	Т				
	R				
	Т				
	R				

ADVERSE EVENTS Table 1. Adverse events reported in the study

STATISTICAL ANALYSIS PLAN

Tables N. Is the adverse event ongoing?/ Relatedness to the medicinal product/ Dose adjustment or temporary withdrawal of the IMP/ Complete withdrawal of the IMP/ Prescribing a concomitant medicinal product/ Prescribing non-drug therapy/ Patient admission to hospital or hospitalization prolongation/ Based on an AE/ Is it an SAE?/ Leads to death/ Threatens life/ Requires admission to hospitalization prolongation/ Leads to permanent or significant incapacity for work or disability

Adverse events	Group	{variable name]	Amount	% of the number of AEs by the medicinal product	p-value, Fisher's test
	Т	value			1
		value			
		value			
All adverse events		value			
	R	value			
		value			
	Т	value			- 1
		value			
SOC		value			
500	R	value			
		value			
		value			
РТ	Т	value			- 1
		value			
		value			
	R	value			
		value			
		value			

STATISTICAL ANALYSIS PLAN

Adverse events	Group	{variable name]	Amount	% of the number of AEs by the medicinal product	p-value, Fisher's test
DT	Т	value			
		value			
		value			1
Г1		value			
	R	value			
		value			
		value			
	Т	value			1
		value			
		value			
	R	value			
		value			
	Т	value			1
		value			
SOC		value			
30C	R	value			
		value			
		value			
РТ	Т	value			
		value			1
		value			I
	R	value			

STATISTICAL ANALYSIS PLAN

Adverse events	Group	{variable name]	Amount	% of the number of AEs by the medicinal product	p-value, Fisher's test
		value			
		value			
		value			1
	Т	value			
DT		value			
P1	R	value			
		value			
		value			
	Т	value			
		value			

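### The SAP omits the protocol's by-arm analysis of on-treatment vital signs and physical findings, drops the AE severity test, and has no table layouts for severity, glucose or abnormal laboratory results

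*SAP*

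**What the plan says.** **Protocol.** Section 9.1.4 sets out four safety analyses.

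- Item 1 covers the number, incidence and severity of AEs. For severity, "a comparison of the severity (and the possible causality between the study drug and AE) will be conducted using the Cochran—Armitage test".
- Item 2 covers gastrointestinal disorders which, when "regarded by the Investigator as related to the study therapy, will be analyzed separately".
- Item 3 covers laboratory changes and abnormal results, compared by arm.
- Item 4 reads: "Changes in the vital signs over time and the incidence of pathological abnormalities revealed during physical examination will be summarized by group", followed by a comparison between the arms.

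The Synopsis and section 4.1 make the same commitments. Section 4.1 also lists as a secondary endpoint: "Frequency and severity of all adverse events observed during the study therapy in the study groups". Section 9.1 leaves the full description of the analysis to the SAP.

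**SAP.** Section 1 states that the plan conforms to the protocol. Section 9 lists physical examination, blood pressure and heart rate among the procedures performed. Section 9.1 then gives analyses for AEs (number, frequency, severity) and for laboratory tests (changes over time, abnormal results), plus one general sentence that safety data will use the efficacy methods. Section 9.2 says: "No other safety endpoints are foreseen in this study".

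**The concern.** The SAP is the document that the programmers and the report will follow. It claims conformance with the protocol, yet two analyses that the protocol states have no counterpart in its safety section. For several others the text makes a promise that the layouts do not carry out.

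The stake is the safety comparison, which is the only secondary objective. The trial is open-label and investigators grade AE severity knowing the treatment. Blood pressure, heart rate and central-laboratory values are therefore a useful objective check on the AE comparison. Laboratory means by visit can look alike in the two arms while the numbers of patients moving out of range differ. Protocol 9.7 requires departures from the original statistical plan to be described and justified; the SAP text gives no reason for these.

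**Working it through.** The plan gives no figure to reproduce, so this is a coverage check. Each promised item is set against the SAP text and the Appendix 1 layouts.

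| Item promised in the protocol | SAP text | SAP layouts |
|---|---|---|
| Vital signs over time, by arm (9.1.4 item 4) | Pre-treatment comparison only (section 5); collection listed in section 9; no specific post-baseline analysis | None |
| Abnormal physical findings, by arm (9.1.4 item 4) | As above | None |
| AE severity, Cochran-Armitage (9.1.4) | Severity to be determined (9.1); no test named for it | None |
| Laboratory changes and abnormal results, by arm (9.1.4 item 3) | Promised in 9.1, no analyte excluded | Visit-level summaries only for the safety tests; glucose absent |

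**Vital signs and findings.** The physiological layouts (Tables 12 to 14) hold weight, age, BMI, height and gender, all at the first visit. None has blood pressure, heart rate or an examination finding.

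**Severity.** Protocol 8.3.2 grades AEs as mild, moderate or severe. The variables for the repeated AE tables begin "Is the adverse event ongoing?/ Relatedness to the medicinal product/ Dose adjustment or temporary withdrawal of the IMP/ Complete withdrawal of the IMP" and continue through other actions taken and the SAE criteria. Severity is not among them. Relatedness is, with a Fisher p-value, so that half of the protocol's trend comparison keeps an output under a different test. Severity has neither a test nor a table.

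**Glucose.** The panel in Protocol Table 5 and the visit descriptions is total protein, total bilirubin, conjugated bilirubin, AST, ALT, alkaline phosphatase, creatinine, glucose and CRP: 9 analytes. It is drawn at screening and Week 12.

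- SAP Table 15 shows ALT, AST, total protein, total bilirubin and CRP: 5.
- SAP Table 16 shows conjugated bilirubin, creatinine and alkaline phosphatase: 3.
- 5 + 3 = 8, and 9 − 8 = 1. The missing analyte is glucose.
- SAP Table 17 holds T4, vitamin B12, creatinine index, TSH and folic acid. Tables 18 to 20 repeat the same variables for the tests.

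**Change and abnormal results.** The efficacy layouts have change-from-screening tables for hemoglobin and the iron parameters. The safety chemistry, hematology and urinalysis layouts have no change columns and no counts of out-of-range results, although SAP 9.1 promises both.

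**Visit schedule.** Protocol Table 5 places physical examination, blood pressure and heart rate at Visits 0, 2, 3 and 4 (four visits, three after baseline). Protocol 8.1 and SAP section 9 give screening, the second visit and the final visit (three visits, two after baseline). An analysis over time needs one answer.

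**Related observation.** The same comparison shows that SAP 9.1 does not carry over the separate analysis of treatment-related gastrointestinal disorders (Protocol 9.1.4 item 2).

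**The case against.** Much of the opposing case stands.

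- **A reader might infer that severity, glucose and abnormal laboratory results would never be analysed.** The documents do not support that. SAP 9.1 names AE severity, and it commits to comparing laboratory changes and abnormal results without excluding any analyte. Glucose is in the SAP's own panel. Nothing says that the layouts limit the text. For glucose and abnormal results the fault is a missing output. For severity it is a missing output and a missing test.
- **A reader might infer that the SAP drops a drug risk which the protocol names.** Protocol 2.3.6.4 does say: "Insignificant increase in iron store concentration is associated with a significant increase in glucose homeostasis parameters". That is an association with iron stores, not an effect of the study drug. The product texts in 2.1.1 and 2.1.2 expect no effect on daily insulin requirement for either product, both arms take the same active substance at the same daily dose of iron, and decompensated diabetes is excluded. The case for a glucose table is that it completes the panel.
- **SAP 9.2 speaks of endpoints, and the protocol's endpoint list names only AE frequency and severity for safety.** Read strictly, 9.2 agrees with that list. But 9.1 does not supply the item 4 analysis either, so nothing in the SAP's safety section does.
- **The general sentence in SAP 9.1 might reach vital signs.** It names methods, not variables. For severity, the categorical methods in SAP 8.2 are chi-square and Fisher tests, which ignore the order of the grades.
- **Clinically significant abnormalities are recorded as AEs (Protocol 8.3.4).** True, but that captures only what the investigator judged significant, not group shifts.
- **A reader might think the laboratory layouts refer to a phone visit, because they use V5.** The layouts number screening as V1 and then use V3, V4 and V5, a consistent one-step offset. This is at most a labelling note.

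**Conclusion.** The concern holds in this form. The SAP omits the post-baseline by-arm analysis of vital signs and abnormal physical findings, and it drops the Cochran-Armitage comparison of AE severity. Its layouts also lack severity, glucose, and change and abnormal-result counts for the safety laboratory tests, although its text still promises severity and the laboratory analyses.

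The size is two protocol analyses without an SAP counterpart (item 4 and the severity test), one of nine chemistry analytes without a table, and one of the two parts of the AE endpoint (severity) without a table. Multiplying patients by visits to count unanalysed readings would overstate it: SAP section 5 covers screening values, the number of visits is itself inconsistent, and dropout is planned for.

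This should be corrected before the analysis, but it does not bear on the non-inferiority result. It assumes that no SAP page outside the text reviewed supplies the missing items. The SAP's front pages were not available and no sections numbered 4.2 or 7 appear in the text, but the visible list of tables and the layouts show none of these outputs.

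**What to change.** 1. Replace the SAP 9.2 statement with the Protocol 9.1.4 item 4 analysis: vital signs over time and abnormal physical findings, summarised and compared by arm, with layouts.
2. Restore the Cochran-Armitage comparison of AE severity in SAP 9.1 and add severity to the repeated AE tables.
3. Add glucose to the screening and Week 12 biochemistry tables and to the matching test table.
4. Add change from screening and counts of abnormal results, by arm, to the safety laboratory layouts, as SAP 9.1 already promises.
5. Reconcile the vital-sign schedule between Protocol Table 5, Protocol 8.1 and SAP section 9.
6. In the same revision, restore the separate analysis of treatment-related gastrointestinal disorders, and add a note mapping the layouts' visit numbers to the protocol visits.

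If any omission is deliberate, record and justify it as Protocol 9.7 requires. The cost is SAP text and a few standard tables, using data the protocol already collects.

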Appendix 1. Table layouts

PRIMARY ENDPOINT

Parameter	Coef.	Standard error	t -value	p -value	С	2I
Constant (intercept)						
Group R versus Group T						
Gender M versus F						
Weight						
Base hemoglobin factor (80–94 g/L compared to 95–110 g/L)						
Hemoglobin level at screening						
Interactions						

SECONDARY ENDPOINTS

Table 1. Hemoglobin, frequency analysis of the treatment efficacy after 12 weeks

Hemoglobin (g/L)					
Group	Parameter	Value			
	Total observations				
$R - Maltofer^{\mathbb{R}}$	Responders, n				
	Responders, %				
	95% CI				
	Total observations				
T – Ferrum Lek®	Responders, n				
	Responders, %				
	95% CI				
Group comparison	Pearson's chi-square test, p-value				

Table 2. Results of analysis of variance

Coefficients	Evaluation	Standard error	t-value	p-value
(Intercept)				
V1_CB_LBORRES_HB				
(Hemoglohin level at screening)				
Group T – Ferrum Lek [®]				
(Test to reference group factor)				

Table 3. Hemoglobin, absolute values, g/L

Hemoglobin (g/L)						
Group	Parameter	Screening	Week 4	Week 8	Week 12	
	Number of observations					
	Number of missing values					
	Mean value					
R – Maltofer®	95% CI					
	Standard deviation					
	Median					
	Minimum value					
	Maximum value					

	1st quartile		
	3rd quartile		
	Interquartile range		
	p-value (Shapiro–Wilk test)		
	Number of observations		
	Number of missing values		
	Mean value		
	95% CI		
	Standard deviation		
	Median		
T – Ferrum Lek [®]	Minimum value		
	Maximum value		
	1st quartile		
	3rd quartile		
	Interquartile range		
	p-value (Shapiro–Wilk test)		
Group	Criterion		
comparison	p-value		

SOP-05-02_RF01 Statistical Analysis Plan_01APR2020_3.0

Table 4. Hemoglobin, changes, g/L

Hemoglobin (g/L)						
Group	Parameter	Week 4 – Screening	Week 8 – Screening	Week 12 – Screening		
	Number of observations					
	Number of missing values					
	Mean value					
	95% CI					
	Standard deviation					
	Median					
R – Maltofer®	Minimum value					
	Maximum value					
	1st quartile					
	3rd quartile					
	Interquartile range					
	p-value (Shapiro–Wilk test)					
	Number of observations					
	Number of missing values					
	Mean value					
T − Ferrum Lek®	95% CI					
	Standard deviation					
	Median					
	Minimum value					

STATISTICAL ANALYSIS PLAN

	Maximum value		
	1st quartile		
	3rd quartile		
	Interquartile range		
	p-value (Shapiro–Wilk test)		
Group comparison	Criterion		
	p-value		

Table 5. Blood serum iron, absolute values, μ mol/L

Serum iron level (µmol/L)						
Group	Parameter	Screening	Week 4	Week 8	Week 12	
	Number of observations					
	Number of missing values					
	Mean value					
D. Maltafar®	95% CI					
K – Manoier	Standard deviation					
	Median					
	Minimum value					
	Maximum value					

STATISTICAL ANALYSIS PLAN

	1st quartile		
	3rd quartile		
	Interquartile range		
	p-value (Shapiro–Wilk test)		
	Number of observations		
	Number of missing values		
	Mean value		
	95% CI		
	Standard deviation		
	Median		
T – Ferrum Lek®	Minimum value		
	Maximum value		
	1st quartile		
	3rd quartile		
	Interquartile range		
	p-value (Shapiro–Wilk test)		
	Criterion		
Group comparison	p-value		

SOP-05-02_RF01 Statistical Analysis Plan_01APR2020_3.0

Table 6. Blood serum iron, changes, µmol/L

Serum iron level (µmol/L)						
Group	Parameter	Week 4 – Screening	Week 8 – Screening	Week 12 – Screening		
	Number of observations					
	Number of missing values					
	Mean value					
	95% CI					
	Standard deviation					
	Median					
R – Maltofer [®]	Minimum value					
	Maximum value					
	1st quartile					
	3rd quartile					
	Interquartile range					
	p-value (Shapiro–Wilk test)					
	Number of observations					
	Number of missing values					
	Mean value					
T – Ferrum Lek®	95% CI					
	Standard deviation					
	Median					
	Minimum value					

STATISTICAL ANALYSIS PLAN

	Maximum value		
	1st quartile		
	3rd quartile		
	Interquartile range		
	p-value (Shapiro–Wilk test)		
Group comparison	Criterion		
	p-value		

Table 7. Transferrin, absolute values, g/L

Transferrin (g/L)					
Group	Parameter	Screening	Week 4	Week 8	Week 12
	Number of observations				
	Number of missing values				
	Mean value				
	95% CI				
	Standard deviation				
	Median				
R – Maltofer®	Minimum value				
	Maximum value				
	1st quartile				
	3rd quartile				
	Interquartile range				
	p-value (Shapiro–Wilk test)				
	Number of observations				
	Number of missing values				
T – Ferrum Lek®	Mean value				
	95% CI				
	Standard deviation				
	Median				

SOP-05-02_RF01 Statistical Analysis Plan_01APR2020_3.0

STATISTICAL ANALYSIS PLAN

	Minimum value		
	Maximum value		
	lst quartile		
	3rd quartile		
	Interquartile range		
	p-value (Shapiro–Wilk test)		
Group comparison	Criterion		
	p-value		

Table 8. Transferrin, changes, g/L

Transferrin (g/L)						
Group	Parameter	Week 4 – Screening	Week 8 – Screening	Week 12 – Screening		
	Number of observations					
	Number of missing values					
	Mean value					
	95% CI					
	Standard deviation					
	Median					
R – Maltofer®	Minimum value					
	Maximum value					
	1st quartile					
	3rd quartile					
	Interquartile range					
	p-value (Shapiro–Wilk test)					
	Number of observations					
	Number of missing values					
T – Ferrum I ek®	Mean value					
	95% CI					
	Standard deviation					
	Median					

STATISTICAL ANALYSIS PLAN

	Minimum value		
	Maximum value		
	1st quartile		
	3rd quartile		
	Interquartile range		
	p-value (Shapiro–Wilk test)		
Group comparison	Criterion		
	p-value		

Table 9. Percentage of transferrin saturation with iron, absolute values (%)

Percentage of transferrin saturation with iron (%)							
Group	Parameter	Screening	Week 4	Week 8	Week 12		
	Number of observations						
	Number of missing values						
	Mean value						
	95% CI						
K – Maltofer®	Standard deviation						
	Median						
	Minimum value						
	Maximum value						

STATISTICAL ANALYSIS PLAN

	1 / /1		
	1st quartile		
	3rd quartile		
	Interquartile range		
	p-value (Shapiro–Wilk test)		
	Number of observations		
	Number of missing values		
	Mean value		
	95% CI		
	Standard deviation		
	Median		
$T-Ferrum \ Lek^{\circledast}$	Minimum value		
	Maximum value		
	1st quartile		
	3rd quartile		
	Interquartile range		
	p-value (Shapiro–Wilk test)		
Carolin agreed in the	Criterion		
Group comparison	p-value		

SOP-05-02_RF01 Statistical Analysis Plan_01APR2020_3.0

Table 10. Percentage of transferrin saturation with iron, changes (%)

Percentage of transferrin saturation with iron (%)							
Group	Parameter	Week 4 – Screening	Week 8 – Screening	Week 12 – Screening			
	Number of observations						
	Number of missing values						
	Mean value						
	95% CI						
	Standard deviation						
	Median						
$R-Maltofer^{\ensuremath{\mathbb{R}}}$	Minimum value						
	Maximum value						
	1st quartile						
	3rd quartile						
	Interquartile range						
	p-value (Shapiro–Wilk test)						
	Number of observations						
	Number of missing values						
T – Ferrum I ek®	Mean value						
i i cirdin Lok	95% CI						
	Standard deviation						
	Median						

SOP-05-02_RF01 Statistical Analysis Plan_01APR2020_3.0

STATISTICAL ANALYSIS PLAN

	Minimum value		
	Maximum value		
	1st quartile		
	3rd quartile		
	Interquartile range		
	p-value (Shapiro–Wilk test)		
Group comparison	Criterion		
Group comparison	p-value		

Table 11. Ferritin, absolute values, $\mu g/L$

Serum ferritin level (µg/L)								
Group	Parameter Screening Week 4 Week 8 Week							
	Number of observations							
	Number of missing values							
	Mean value							
	95% CI							
	Standard deviation							
	Median							
R – Maltofer®	Minimum value							
	Maximum value							
	1st quartile							
	3rd quartile							
	Interquartile range							
	p-value (Shapiro–Wilk test)							
	Number of observations							
T – Ferrum Lek®	Number of missing values							
	Mean value							
	95% CI							

		1	r	
	Standard deviation			
	Median			
	Minimum value			
	Maximum value			
	1st quartile			
	3rd quartile			
	Interquartile range			
	p-value (Shapiro–Wilk test)			
Group comparison	Criterion			
Group comparison	p-value			

Table 12. Ferritin, changes, µg/L

Serum ferritin level (µg/L)								
Group	Parameter	Week 4 – Screening	Week 8 – Screening	Week 12 – Screening				
	Number of observations							
	Number of missing values							
	Mean value							
	95% CI							
	Standard deviation							
	Median							
R – Maltofer [®]	Minimum value							
	Maximum value							
	1st quartile							
	3rd quartile							
	Interquartile range							
	p-value (Shapiro–Wilk test)							
	Number of observations							
	Number of missing values							
T Ferrum Lek®	Mean value							
I – I CITUIII LEK	95% CI							
	Standard deviation							
	Median							

STATISTICAL ANALYSIS PLAN

	Minimum value		
	Maximum value		
	1st quartile		
	3rd quartile		
	Interquartile range		
	p-value (Shapiro–Wilk test)		
Group comparison	Criterion		
	p-value		

STATISTICAL ANALYSIS PLAN

LABORATORY RESULTS

Table 1. Urinalysis

Visit	Group	Parameter	рН	Protein	Specific gravity	RBC
		N				
		Missed				
		Beyond the limit of detection				
		Mean				
		95% CI				
	Treatment group:	SD				
	K – Manoler	Median				
171		Min				
V I		Max				
		Q1.25%				
		Q3.75%				
		IQR.75%				
		Ν				
	Tractment crown.	Missed				
	T – Ferrum Lek [®]	Beyond the limit of detection				
		Mean				

STATISTICAL ANALYSIS PLAN

Visit	Group	Parameter	рН	Protein	Specific gravity	RBC
		95% CI				
		SD				
		Median				
		Min				
		Max				
		Q1.25%				
		Q3.75%				
		IQR.75%				
		Ν				
		Missed				
		Beyond the limit of detection				
		Mean				
		95% CI				
	Treatment group:	SD				
V5	$\mathbf{K} = \mathbf{M}\mathbf{a}\mathbf{H}\mathbf{O}\mathbf{I}\mathbf{e}\mathbf{r}^{-1}$	Median				
		Min				
		Max				
		Q1.25%				
		Q3.75%				
		IQR.75%				
		N				

SOP-05-02_RF01 Statistical Analysis Plan_01APR2020_3.0 Confidential Page 41 of 68

STATISTICAL ANALYSIS PLAN

Visit	Group	Parameter	рН	Protein	Specific gravity	RBC
		Missed				
		Beyond the limit of detection				
		Mean				
		95% CI				
	Treatment group:	SD				
	$T - Ferrum Lek^{\otimes}$	Median				
		Min				
		Max				
		Q1.25%				
		Q3.75%				
		IQR.75%				

Table 2. Urinalysis statistical test

Vis	sit	V1	V5	V1	V5	V1	V5	V1	V5
Varia	able	p	Н	Pro	otein	Specific	Specific gravity RBC		BC
Shapiro–Wilk test, p-value	Treatment group: R – Maltofer [®] Treatment group: T – Ferrum Lek [®]								
Student's t-te	est, p-value								
Wilcoxon-Mann-W	hitney test, p-value								

STATISTICAL ANALYSIS PLAN

Table 3. Urinalysis, categorical variables

Visit	Variable	Group	Distribution of responses	Chi-square test, p-value
	WDC	$\begin{array}{l} \text{Treatment group:} \\ \text{R}-\text{Maltofer}^{\texttt{®}} \end{array}$		
V1	WBC	Treatment group: T – Ferrum Lek [®]		
V I	Color	$\begin{array}{l} Treatment \ group: \\ R-Maltofer^{\circledast} \end{array}$		
		Treatment group: T – Ferrum Lek [®]		
	WDC	$\begin{array}{l} Treatment \ group: \\ R-Maltofer^{\circledast} \end{array}$		
V5	WBC	Treatment group: T – Ferrum Lek [®]		
	Color	$\begin{array}{c} \text{Treatment group:} \\ \text{R}-\text{Maltofer}^{\circledast} \end{array}$		
		Treatment group: T – Ferrum Lek [®]		

Table 4. Hematology 1

Visit	Group	Parameter	Hematocrit (%)	Hemoglobin	RBC
V1 Treatment g R – Malto		Ν			
	Tractment group	Missed			
	R – Maltofer [®]	Beyond the limit of detection			
		Mean			

SOP-05-02_RF01 Statistical Analysis Plan_01APR2020_3.0 Confidential Page 43 of 68

STATISTICAL ANALYSIS PLAN

Visit	Group	Parameter	Hematocrit (%)	Hemoglobin	RBC
		95% CI			
		SD			
		Median			
		Min			
		Max			
		Q1.25%			
		Q3.75%			
		IQR.75%			
		N			
		Missed			
		Beyond the limit of detection			
		Mean			
		95% CI			
	Treatment group:	SD			
	$T-Ferrum \ Lek^{\circledast}$	Median			
		Min			
		Max			
		Q1.25%			
		Q3.75%			
		IQR.75%			
1/2	Treatment group:	N			
٧3	$R-Maltofer^{\ensuremath{\mathbb{R}}}$	Missed			

STATISTICAL ANALYSIS PLAN

Visit	Group	Parameter	Hematocrit (%)	Hemoglobin	RBC
		Beyond the limit of detection			
		Mean			
		95% CI			
		SD			
		Median			
		Min			
		Max			
		Q1.25%			
		Q3.75%			
		IQR.75%			
		Ν			
		Missed			
		Beyond the limit of detection			
		Mean			
	Treatment group.	95% CI			
	$T - Ferrum Lek^{\mathbb{R}}$	SD			
		Median			
		Min			
		Max			
		Q1.25%			
		Q3.75%			

SOP-05-02_RF01 Statistical Analysis Plan_01APR2020_3.0 Confidential Page 45 of 68

STATISTICAL ANALYSIS PLAN

Visit	Group	Parameter	Hematocrit (%)	Hemoglobin	RBC
		IQR.75%			
		Ν			
		Missed			
		Beyond the limit of detection			
		Mean			
		95% CI			
	Treatment group:	SD			
	K – Mattoler	Median			
		Min			
		Max			
774		Q1.25%			
V4		Q3.75%			
		IQR.75%			
		Ν			
		Missed			
		Beyond the limit of detection			
	Treatment group:	Mean			
	1 – Ferrum Lek [®]	95% CI			
		SD			
		Median			
		Min			

SOP-05-02_RF01 Statistical Analysis Plan_01APR2020_3.0 Confidential Page 46 of 68

STATISTICAL ANALYSIS PLAN

Visit	Group	Parameter	Hematocrit (%)	Hemoglobin	RBC
		Max			
		Q1.25%			
		Q3.75%			
		IQR.75%			
		N			
		Missed			
		Beyond the limit of detection			
		Mean			
	Treatment group: R – Maltofer [®]	95% CI			
		SD			
		Median			
		Min			
V5		Max			
		Q1.25%			
		Q3.75%			
		IQR.75%			
		Ν			
		Missed			
	Treatment group: T – Ferrum Lek®	Beyond the limit of detection			
		Mean			
		95% CI			

SOP-05-02_RF01 Statistical Analysis Plan_01APR2020_3.0 Confidential Page 47 of 68

STATISTICAL ANALYSIS PLAN

Visit	Group	Parameter	Hematocrit (%)	Hemoglobin	RBC
		SD			
		Median			
		Min			
		Max			
		Q1.25%			
		Q3.75%			
		IQR.75%			

Table 5. Hematology 2

Visit	Group	Parameter	WBC	Lymphocytes	Lymphocytes (%)
		N			
		Missed			
		Beyond the limit of detection			
		Mean			
		95% CI			
V1	Treatment group:	SD			
	K – Maltoler®	Median			
		Min			
		Max			
		Q1.25%			
		Q3.75%			
		IQR.75%			

SOP-05-02_RF01 Statistical Analysis Plan_01APR2020_3.0 Confidential Page 48 of 68

STATISTICAL ANALYSIS PLAN

Visit	Group	Parameter	WBC	Lymphocytes	Lymphocytes (%)
		N			
		Missed			
		Beyond the limit of detection			
		Mean			
		95% CI			
	Treatment group:	SD			
	I – Perfulli Lek	Median			
		Min			
		Max			
		Q1.25%			
		Q3.75%			
		IQR.75%			

Table 6. Hematology 3

Visit	Group	Parameter	Neutrophils	Neutrophils (%)	Stab neutrophils (%)	Segmented neutrophils (%)
		Ν				
		Missed				
V1	Treatment group:	Beyond the limit of detection				
	R – Maltofer®	Mean				
		95% CI				
		SD				

STATISTICAL ANALYSIS PLAN

Visit	Group	Parameter	Neutrophils	Neutrophils (%)	Stab neutrophils (%)	Segmented neutrophils (%)
		Median				
		Min				
		Max				
		Q1.25%				
		Q3.75%				
		IQR.75%				
		Ν				
		Missed				
		Beyond the limit of detection				
		Mean				
		95% CI				
	Treatment group:	SD				
	I – Fellulli Lek	Median				
		Min				
		Max				
		Q1.25%				
		Q3.75%				
		IQR.75%				

STATISTICAL ANALYSIS PLAN

Table 7. Hematology 4

Visit	Group	Parameter	Basophils	Basophils (%)	ESR	Platelets	Eosinophils	Eosinophils (%)
		Ν						
		Missed						
		Beyond the limit of detection						
		Mean						
	T	95% CI						
	R – Maltofer [®]	SD						
		Median						
		Min						
V1		Max						
V I		Q1.25%						
		Q3.75%						
		IQR.75%						
		Ν						
		Missed						
	Treatment group:	Beyond the limit of detection						
		Mean						
		95% CI						
		SD						

SOP-05-02_RF01 Statistical Analysis Plan_01APR2020_3.0 Confidential Page 51 of 68

STATISTICAL ANALYSIS PLAN

Visit	Group	Parameter	Basophils	Basophils (%)	ESR	Platelets	Eosinophils	Eosinophils (%)
		Median						
		Min						
		Max						
		Q1.25%						
		Q3.75%						
		IQR.75%						

STATISTICAL ANALYSIS PLAN

Table 8. Hematology, statistical test 1

Vi	sit	V1	V3	V4	V5	V1	V3	V4	V5	V1	V3	V4	V5
Vari	able		Hemato	ocrit (%)			Hemo	globin			RBC		
Shapiro– Wilk test, p- value	Treatment group: R – Maltofer®												
	Treatment group: T – Ferrum Lek®												
Student's t-test, p-value													
Wilcoxon–Mann–Whitney test, p- value													

Table 9. Hematology, statistical test 2

sit	V1			
Variable			Lymphocytes (%)	
Treatment group: R – Maltofer®				
Treatment group: T – Ferrum Lek [®]				
est, p-value				
/hitney test, p-value				
	sit able Treatment group: R – Maltofer [®] Treatment group: T – Ferrum Lek [®] est, p-value /hitney test, p-value	sitableWBCTreatment group: $R - Maltofer^{\ensuremath{\mathbb{R}}}$ Treatment group: $T - Ferrum Lek^{\ensuremath{\mathbb{R}}}$ est, p-value/hitney test, p-value	sit $V1$ ableWBCLymphocytesTreatment group: $R - Maltofer^{®}$ Treatment group: $T - Ferrum Lek^{®}$ est, p-value/hitney test, p-value	

Table 10. Hematology, statistical test 3

Visit	V1	
-------	----	--

SOP-05-02_RF01 Statistical Analysis Plan_01APR2020_3.0 Confidential Page 53 of 68

STATISTICAL ANALYSIS PLAN

Vari	Neutrophils	Neutrophils (%)	Stab neutrophils (%)	Segmented neutrophils (%)	
Shapiro– Wilk test, p-value	Treatment group: R – Maltofer [®]				
	Treatment group: T – Ferrum Lek®				
Student's t-t					
Wilcoxon–Mann–W	/hitney test, p-value				

Table 11. Hematology, statistical test 4

Vi	V1						
Variable		Basophils	Basophils (%)	ESR	Platelets	Eosinophils	Eosinophils (%)
Shapiro–Wilk test, p-value	Treatment group: R – Maltofer [®]						
	Treatment group: T – Ferrum Lek®						
Student's t-test, p-value							
Wilcoxon–Mann–W	/hitney test, p-value						

Table 12. Physiological data

Visit	Group	Parameter	Weight	Age	BMI	Height
V1	Treatment group:	Ν				
V I	$R-Maltofer^{\mbox{\tiny (\sc R)}}$	Missed				

SOP-05-02_RF01 Statistical Analysis Plan_01APR2020_3.0 Confidential Page 54 of 68

STATISTICAL ANALYSIS PLAN

Visit	Group	Parameter	Weight	Age	BMI	Height
		Beyond the limit of detection				
		Mean				
		95% CI				
		SD				
		Median				
		Min				
		Max				
		Q1.25%				
		Q3.75%				
		IQR.75%				
		Ν				
		Missed				
		Beyond the limit of detection				
		Mean				
	Treatment group:	95% CI				
	T – Ferrum Lek [®]	SD				
		Median				
		Min				
		Max				
		Q1.25%				
		Q3.75%				

STATISTICAL ANALYSIS PLAN

Visit	Group	Parameter	Weight	Age	BMI	Height
		IQR.75%				

Table 13. Physiological data, statistical test

Vi	V1				
Vari	Weight	Age	BMI	Height	
Shapiro– Wilk test, p-value	Treatment group: R – Maltofer [®]				
	Treatment group: T – Ferrum Lek [®]				
Student's t-					
Wilcoxon–Mann–W					

Table 14. Physiological data, categorical data

Visit	Variable	Group	Distribution of responses	Chi-square test, p-value
7/1	Conton	Treatment group: $R - Maltofer^{$		
V1	Gender	Treatment group: T – Ferrum Lek®		

Table 15. Biochemistry 1

Visit	Group	Parameter	ALT	AST	Total protein	Total bilirubin	C-reactive protein
V1	Treatment group:	Ν					
	$R - Maltofer^{\mathbb{R}}$	Missed					

STATISTICAL ANALYSIS PLAN

Visit	Group	Parameter	ALT	AST	Total protein	Total bilirubin	C-reactive protein
		Beyond the limit of detection					
		Mean					
		95% CI					
		SD					
		Median					
		Min					
		Max					
		Q1.25%					
		Q3.75%					
		IQR.75%					
		Ν					
		Missed					
		Beyond the limit of detection					
		Mean					
	Treatment group:	95% CI					
	I – Ferrum Lek	SD					
		Median					
		Min					
		Max					
		Q1.25%					

SOP-05-02_RF01 Statistical Analysis Plan_01APR2020_3.0

STATISTICAL ANALYSIS PLAN

Visit	Group	Parameter	ALT	AST	Total protein	Total bilirubin	C-reactive protein
		Q3.75%					
		IQR.75%					
		Ν					
		Missed					
		Beyond the limit of detection					
		Mean					
		95% CI					
	Treatment group: R – Maltofer®	SD					
		Median					
		Min					
1/5		Max					
V 5		Q1.25%					
		Q3.75%					
		IQR.75%					
		Ν					
		Missed					
	Treatment group:	Beyond the limit of detection					
	I – Ferrum Lek®	Mean					
		95% CI					
	·	SD					

SOP-05-02_RF01 Statistical Analysis Plan_01APR2020_3.0

STATISTICAL ANALYSIS PLAN

Visit	Group	Parameter	ALT	AST	Total protein	Total bilirubin	C-reactive protein
		Median					
		Min					
		Max					
		Q1.25%					
		Q3.75%					
		IQR.75%					

Table 16. Biochemistry 2

